5.1 Collection and Derivation of Efficacy Assessments

The MAS-B will be used to evaluate spasticity of each of the injected muscle groups (elbow flexors, wrist flexors and finger flexors) based on rating the resistance encountered in a specific muscle group by means of passively moving a limb through its range of motion at a specified velocity.

At day 1 and weeks 2, 4, 6, 8 and 12, the same investigator (when possible) will assess the patient's upper limb muscle tone. For the elbow or wrist flexor muscles, the investigator will passively extend the patient's affected elbow/wrist from a position of maximum possible flexion to a maximal possible extension. The resistance encountered to the passive stretch will be rated on the MAS-B as follows:

0 =	No increase in muscle tone
1 =	Slight increase in muscle tone, manifested by a catch and release, or by minimal resistance at the end of the range of motion when the affected part(s) is moved in flexion or extension
1+ =	Slight increase in muscle tone, manifested by a catch, followed by minimal resistance throughout the remainder (less than half) of the range of motion
2 =	More marked increase in muscle tone through most of the range of motion, but affected part(s) easily moved. There can be a catch, but movement should be stiff through most of range.
3 =	Considerable increase in muscle tone, passive movement difficult
4 =	Affected part(s) rigid in flexion or extension

[figure not shown]
The MAS-B scores of 0, 1, 1+, 2, 3, or 4 will be coded as a grade of 0, 1, 2, 3, 4, or 5, respectively. The MAS-B grade change from baseline to each post-randomization visit and the primary endpoint, average change from baseline at weeks 4 and 6, will be derived for each patient for elbow flexors and wrist flexors muscle groups. Additionally, a responder status will be determined according to whether or not a patient has at least a 1-grade reduction from baseline in MAS-B.

[figure not shown]
The CGI by Physician will be measured at weeks 2, 4, 6, 8, and 12. There is no CGI assessment at baseline. The CGI is a 9-point scale from -4 (very marked worsening) to +4 (very marked improvement). Each assessment is evaluated relative to the patient's baseline status obtained at day 1. The secondary endpoint for CGI will be the average of weeks 4 and 6 scores. Additionally, a responder status will be determined according to whether or not a patient has at least +1 score of CGI by Physician.

The secondary efficacy measures of MAS-B of the finger flexor muscle group, GAS, and MTS will also be collected at scheduled office visits according to the Schedule of Visits and Procedures in the protocol.

MAS-B of the finger flexor muscle group will be collected and derived in the same way as the principal muscle groups.

The GAS is used to measure functional goal attainment relative to the effect of the study intervention. The achievement of 2 functional goals, one active and one passive, preset at week -2 by the patient and family in consultation with the investigator and/or treating occupational/physical therapist relative to the upper limb impairment due to spasticity and confirmed at day 1, will be assessed at weeks 8 and 12 using a scale of -3 (worse than start) to +2 (improvements clearly exceed the defined therapeutic goal).

5.2 Primary Efficacy Analyses

5.2.1 Primary Analyses of Primary Efficacy Variable

The primary efficacy analyses will be based on the mITT population. The primary analysis will be conducted for the average of change from baseline in MAS-B score of the principal muscle group at weeks 4 and 6. For the assessment of treatment groups in the primary endpoint, the statistical null hypothesis is that both BOTOX higher dose (6 U/kg) and lower dose (3 U/kg) have the same mean as placebo. The alternative hypothesis is that at least one study dose of BOTOX has a different mean than placebo. The hypothesis will be tested using Mixed Model Repeated Measures (MMRM) at significance level of 0.05. The primary variable will be summarized by treatment group. The differences of each BOTOX dose group and the placebo group will be used to test the null hypothesis. The analysis will include weeks 2, 4, 6, 8, 12 data. The model will include baseline MAS-B as a covariate and factors of age group, principal muscle group, treatment group, visit, treatment-by-visit interaction, study center, and previous botulinum toxin exposure. Age group and principal muscle group are represented by stratification categories (≤ 6 years and > 6 years for age group, elbow flexors and wrist flexors for designated principal muscle group). Baseline MAS-B grade is a continuous variable included as a covariate. Pooled study center will be produced to ensure each contains at least 12 patients. Pooling method is described in the Section 2.3.

A gate-keeping approach will be used to control the type I error rate for the primary endpoint. Specifically, 6 U/kg versus placebo will be tested first followed by the 3 U/kg versus placebo comparison, each at 2-sided 0.05 level. The 3 U/kg versus placebo comparison will only be performed if the test for 6 U/kg versus placebo is statistically significant.

The co-primary analyses for US FDA only is described in Section 10.

5.2.2 Other Analyses of Primary Efficacy Variable

For sensitivity analysis purposes to supplement the primary analyses, an analysis of covariance (ANCOVA) model using MI for missing values will be conducted. A summary of the percentage of missing MAS-B scores by visit will also be provided. The ANCOVA will include baseline MAS-B score as a covariate and factors of age group, principal muscle group, treatment group, study center and previous botulinum toxin exposure.

The ANCOVA model will be used to analyze each imputation dataset obtained from MI as described in Section 5.1. [REDACTED] will then be used to pool the analyses results across the imputation datasets and produce final parameter estimates. Additional sensitivity analyses for the MAS-B changes from baseline at each assessment time point will also be performed using the same ANCOVA as specified above with observed data, and linear contrasts will be used to estimate the treatment differences between each study dose and placebo.

In addition, the frequency distribution of the grade changes from baseline on the MAS-B, as well as the percentage of responders (with at least a 1-grade reduction in MAS-B), will be summarized by treatment group at each post-treatment office visit. A logistic regression analysis will also be performed on the responder status at each post-treatment visit with a covariate of baseline MAS-B and factors of age group, principal muscle group, treatment group, study center, and previous botulinum toxin exposure, if applicable. The additional analyses will be conducted using observed cases unless stated otherwise.

5.3 Secondary Efficacy Analyses

For secondary efficacy analyses, the observed cases will be used unless stated otherwise.

5.3.1 CGI by Physician

CGI by Physician will be rated at study weeks 2, 4, 6, 8, and 12. Descriptive statistics will be presented by treatment group at each assessment timepoint and for the average of weeks 4 and 6.

CGI by Physician will be summarized and analyzed by MMRM, as well as ANCOVA at each assessment timepoint using observed cases. MMRM model will include baseline MAS-B as a covariate and factors of age group, principal muscle group, treatment group, visit, treatment-by-visit interaction, study center, and previous botulinum toxin exposure. The frequency distribution of the CGI scores, as well as the percentage of responders (CGI score ≥ 1), will be summarized by treatment group at each post-treatment visit. A logistic regression analysis will also be performed on the responder status at each post-treatment visit with factors of age group, principal muscle group, treatment group, study center, and previous botulinum toxin exposure, if applicable.

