5.4 Treatment Allocation Ratio and Stratification

A centralized randomization scheme stratified by age group, principal muscle group, and baseline MAS-B will be prepared by Allergan. Patients will be randomized to 1 of the 3 treatment groups in a 1:1:1 ratio within each combination of strata. Randomization will be dispensed by the IVRS/IWRS. The stratification categories are as follows:

- Age (\leq 6 years and $>$ 6 years)
- Designated principal muscle group (elbow flexors and wrist flexors)
- Baseline (day 1) MAS-B score of the principal muscle group (MAS-B = 2 and MAS-B $>$ 2)

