7.3.2 Secondary Efficacy Analyses

The observed cases will be used for secondary efficacy analyses unless stated otherwise. CGI by Physician will be rated at study weeks 2, 4, 6, 8, and 12. CGI by Physician will be summarized and analyzed by ANCOVA as the average of values at weeks 4 and 6 using the MI method for missing values, as well as at each assessment timepoint using observed cases. The frequency distribution of the CGI scores, as well as the percentage of responders (CGI score of at least +1), will be summarized by treatment group at each posttreatment timepoint. A logistic regression analysis will also be performed on the responder status at each posttreatment timepoint with factors age group, principal muscle group, treatment group, study center, and previous botulinum toxin exposure, if applicable.

The average grade change from baseline for weeks 4 and 6 in the MAS-B for finger flexor muscle groups will be summarized by treatment group and analyzed by ANCOVA using the subgroup of patients with wrist identified as the principal muscle group. The grade change from baseline in the MAS-B for finger flexor muscle groups at each timepoint will also be summarized by treatment group and analyzed by ANCOVA using the same subgroup. The ratings for each of the 2 goals using GAS at weeks 8 and 12 will be summarized by treatment group and analyzed by ANCOVA as specified in Section 7.3.1 to assess the treatment differences. For MTS, the difference between slow and fast motion (R2 - R1) and the individual R2 and R1 values in degrees for the principal muscle group, as well as the respective changes from baseline, will be summarized by treatment group and analyzed by ANCOVA.

[REDACTED]

[REDACTED]

[REDACTED]

[REDACTED]

[REDACTED]

[REDACTED]

[REDACTED]

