1.1 Primary Study Objectives and Design

The primary objective of the study is to evaluate the safety and efficacy of a single treatment of 2 doses (3 U/kg and 6 U/kg) of BOTOX with standardized occupational therapy (OT) in pediatric patients with upper limb spasticity.

This is a multicenter, randomized, double-blind, placebo-controlled, parallel-group, 12-week study evaluating 2 doses of BOTOX, 6 U/kg, 3 U/kg, and placebo with standardized OT for the treatment of monoplegic, hemiplegic, or triplegic children with upper limb spasticity due to cerebral palsy or stroke.

A centralized randomization scheme stratified by age group, principal muscle group, and baseline modified Ashworth Scale – Bohannon (MAS-B) will be used. Patients will be randomized to 1 of 3 treatment groups in a 1:1:1 ratio within each combination of strata. The stratification categories are as follows:

1. Age (≤ 6 years and > 6 years)
2. Designated principal muscle group (elbow flexors and wrist flexors)
3. Baseline (day 1) MAS-B score of the principal muscle group (MAS-B = 2 and MAS-B > 2)

There will be 1 treatment cycle in the study. The maximum study duration per patient will be approximately 16 weeks (including up to 4 weeks in the screening period). Patients will complete 8 study visits as follows: screening (week -4 to week -2), initiation of standardized OT (week -2), randomization and treatment visit (day 1), and post-injection follow-up visits at weeks 2, 4, 6, 8, and 12. All patients will receive weekly OT sessions from week 2 through week 11.

Patients who successfully complete this study without major protocol deviations (eg, non-compliance to protocol required procedures) will be given the option of enrolling in open-label extension Study 191622-105 if they meet eligibility criteria.

Sample size calculation and power consideration are presented in Section 7.5 of the study protocol.

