5.3.3 Global Attainment Scale by Investigator/Therapist

Each of the 2 goals for each patient at each visit will be analyzed by an ANCOVA model with age group, principal muscle group, treatment group, study center and previous botulinum toxin exposure as factors and baseline MAS-B as a covariate to assess treatment differences. The frequency distribution of raw scores for each goal will be summarized by treatment group. Additionally, the percentages of responders who scored 0 or higher (meet or exceed expectation) and the responders who scored -1 or high (slight improvement but not meet expectation) on each functional goal will also be summarized and responder status will be analyzed by logistic regression with factors of age group, principal muscle group, treatment group, study center and previous botulinum toxin exposure, if applicable.

5.3.4

Modified Tardieu Scale of the Principal Muscle Groups

The change from baseline of the angle difference, R2-R1, and the individual R1 and R2 respective changes from baseline will be derived at each post-treatment visit and summarized by treatment group. An ANCOVA model with age group, principal muscle group, treatment group, study center and previous botulinum toxin exposure as factors and baseline MTS as a covariate will be performed to assess treatment differences. The raw scores of R2-R1, R2 and R1 will also be summarized and analyzed using similar methods.

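### The CGI and GAS responder logistic models leave out baseline MAS-B, a stratification factor that the matching mean-score models include

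*SAP*

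**What the plan says.** Protocol 5.4 sets the design: "A centralized randomization scheme stratified by age group, principal muscle group, and baseline MAS-B will be prepared by Allergan". SAP 1.1 repeats the three factors, the third being "Baseline (day 1) MAS-B score of the principal muscle group", split at 2 versus above 2.

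The mean-score analyses of CGI and GAS adjust for it. For CGI (SAP 5.3.1): "MMRM model will include baseline MAS-B as a covariate and factors of age group, principal muscle group, treatment group, visit". For GAS (SAP 5.3.3), the ANCOVA terms include "treatment group, study center and previous botulinum toxin exposure as factors and baseline MAS-B as a covariate to assess treatment differences".

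By contrast, the responder analyses of these two measures do not. For CGI, SAP 5.3.1 has the regression "performed on the responder status at each post-treatment visit with factors of age group, principal muscle group, treatment group, study center"; earlier toxin exposure is the only further term. Protocol 7.3.2 lists the same terms for the CGI responder model: "with factors age group, principal muscle group, treatment group, study center, and previous botulinum toxin exposure, if applicable". For GAS, the responder regression in SAP 5.3.3 names the same five factors and no covariate.

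SAP 5.2.2, on the other hand, specifies the responder model for MAS-B itself "with a covariate of baseline MAS-B and factors of age group, principal muscle group, treatment group, study center". Neither document says why the CGI and GAS responder models differ.

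**The concern.** Two of the three stratification factors are carried into these regressions and the third is dropped. Two analyses of the same measure, listed in the same SAP section, therefore condition on different variables.

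If baseline MAS-B predicts response, leaving it out of a logistic model changes what the odds ratio estimates. The ratio is then conditional on fewer covariates and lies nearer 1. This is non-collapsibility, not bias. The stratified allocation keeps the arms balanced on MAS-B, but the model does not use that balance, so the nominal test tends to be conservative. If baseline MAS-B is not prognostic, nothing is lost.

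These are supportive, observed-case, per-visit analyses outside the gatekeeping procedure (SAP 5.2.1) and the Hochberg procedure (SAP 10.1). CGI is nevertheless a co-primary measure for the US FDA, so its responder odds ratios will be read beside the mean-score result.

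**Working it through.** **Model terms side by side**

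| Analysis | Age group | Principal muscle group | Baseline MAS-B |
|---|---|---|---|
| CGI MMRM (SAP 5.3.1) | yes | yes | yes |
| CGI responder logistic (SAP 5.3.1, protocol 7.3.2) | yes | yes | **no** |
| GAS ANCOVA (SAP 5.3.3) | yes | yes | yes |
| GAS responder logistic (SAP 5.3.3) | yes | yes | **no** |
| MAS-B responder logistic (SAP 5.2.2) | yes | yes | yes |

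**The plan's own figures.** The plan states power only for the mean scores (protocol 7.5): 86% for MAS-B, 94% for CGI, 81% overall. With n = 71 per arm the noncentrality is δ/(σ√(2/n)).
- MAS-B: 0.5/(0.98 × √(2/71)) = 3.04, giving power 85.5% (t) or 86.0% (normal).
- CGI: 0.6/(1.02 × √(2/71)) = 3.50, giving 93.6% (t) or 93.9% (normal).
- Overall: 0.86 × 0.94 = 80.8%.

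The figures reproduce, and none depends on the responder models.

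**Inputs for the size of the effect.** From the documents: 71 per arm (protocol 7.5) and about 30% with baseline MAS-B of 3 or more (protocol 5.5 target). Assumed: placebo response 40%, treatment odds ratio 2.5 within MAS-B stratum, higher MAS-B lowering response, and 17 pooled centres. Seventeen is the most the pooling rule allows with 213 patients, since 213/12 = 17.75.

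**Odds ratio shift (exact, large-sample).** Mix the two strata 70:30, set the intercept to give the placebo rate, and compare arms. At prognostic odds ratio 5:
- Placebo odds are 1 (low stratum) and 1/5 (high stratum). Response = 0.7 × 1/2 + 0.3 × 1/6 = 0.40.
- Treated odds are 2.5 and 0.5. Response = 0.7 × 2.5/3.5 + 0.3 × 0.5/1.5 = 0.60.
- Collapsed odds ratio = (0.60/0.40)/(0.40/0.60) = 2.25, against 2.50 within stratum.

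With placebo response from 30% to 50%, the collapsed value is 2.45 to 2.44 at prognostic odds ratio 2, and 2.29 to 2.23 at 5. If higher MAS-B raises response instead, the value at 40% placebo response and prognostic odds ratio 5 is again 2.25.

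**Power and type I error (simulation).** 5,000 trials per scenario, permuted blocks within the 8 strata, two-sided Wald test at 0.05 for 6 U/kg versus placebo. The models contain treatment, age, muscle group, previous exposure and 17 centres, with and without the binary MAS-B stratum; there is no true centre effect.

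| Prognostic odds ratio | Odds ratio without MAS-B (exact) | Power without / with (%) | Difference (points) | Type I error without / with (%) |
|---|---|---|---|---|
| 1 | 2.50 | 75.9 / 76.0 | 0.1 | 5.4 / 5.4 |
| 1.5 | 2.48 | 74.9 / 75.4 | 0.5 | not run |
| 2 | 2.45 | 74.2 / 75.0 | 0.8 | 5.6 / 5.9 |
| 3 | 2.37 | 71.8 / 73.9 | 2.1 | not run |
| 4 | 2.30 | 70.1 / 73.6 | 3.5 | not run |
| 5 | 2.25 | 66.1 / 70.8 | 4.7 | 4.7 / 6.1 |

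The standard error of each power difference is 0.1 to 0.3 points. A simpler two-arm illustration without centre terms (placebo response 60%, conditional odds ratio 2.0) gave an odds ratio of 1.83 and power of 38.5% without versus 45.0% with the covariate at prognostic odds ratio 5.

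**Size-matched comparison.** At prognostic odds ratio 5 the two tests do not reject equally often under the null, so part of the nominal gap is test size. A separate run of 12,000 trials per scenario, with 3 U/kg in the model and even splits of the other factors, calibrated both tests to 5%. Power without / with MAS-B was:
- prognostic odds ratio 2: 73.0 / 73.0%
- prognostic odds ratio 3: 71.6 / 71.4%
- prognostic odds ratio 5: 68.7 / 68.5%
- prognostic odds ratio 1/5: 67.5 / 68.9%

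**Number of centres.** In a further simulation at prognostic odds ratio 5, type I error without / with MAS-B was 4.6 / 6.1% with 17 centres and 3.9 / 5.0% with 8. Power was 67 / 72% and 67 / 71%.

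**The case against.** The best case for leaving the plan alone has four parts.

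1. *Nothing decisive depends on it.* The gatekeeping and Hochberg tests use MMRM p-values that already adjust for baseline MAS-B. This stands and limits the point to a minor one.
2. *The power loss is mostly test size.* With both tests held to 5%, the gain is about zero, or 1.4 points in the most extreme reversed case. With 17 centres the adjusted test also runs a little above 5%. The first part stands, so the nominal 4.7 points should not be read as lost information. The excess, however, fits the many centre terms, because it disappears with 8 centres. There the adjusted test holds 5.0% while the test without MAS-B is conservative at 3.9%.
3. *There may be a pattern.* Responder models may carry the outcome's own baseline where one exists. CGI has none (SAP 5.1), and GAS is scored relative to the starting condition (protocol 12.1.12). The finger-flexor models (SAP 5.3.2) and the MTS ANCOVA (SAP 5.3.4) also omit principal-muscle MAS-B and use their own baselines. So the plan does not put every stratification factor in every model. The pattern still does not explain this gap, because the CGI MMRM and GAS ANCOVA use baseline MAS-B despite having no baseline of their own. The closing proviso about applicability does not help either, since baseline MAS-B is not in the list that it qualifies.
4. *A mean difference and a per-visit odds ratio are different estimands anyway.* This is true, but it gives no reason to drop a stratification factor from one of them.

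**Conclusion.** The inconsistency is real and unexplained. For CGI it starts in protocol 7.3.2 and carries into the SAP; for GAS it is in the SAP. Its consequence is small. At a prognostic odds ratio of 2 or less, the treatment odds ratio moves from 2.50 to no lower than about 2.45, and nominal power falls by at most 0.8 points. At 5 the figures are 2.25 and 4.7 points, with almost no difference once test size is matched.

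The omission does not inflate type I error, and no primary or co-primary conclusion depends on it. All sizes rest on the assumed placebo response, treatment effect and prognostic strength, and the simulations used the two-level stratum rather than the MAS-B grade. This is an optional, nearly free improvement that brings two supportive models into line with the randomization and with the other models in the plan.

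**What to change.** Add baseline MAS-B of the principal muscle group as a covariate to the CGI responder logistic model (SAP 5.3.1 and protocol 7.3.2) and to the GAS responder logistic model (SAP 5.3.3), as the MAS-B responder model in SAP 5.2.2 already does. Name the form in the text; the continuous grade used in SAP 5.2.1 would keep the models consistent. The cost is one covariate and one degree of freedom in each of two models. The data are already collected, and no sample-size figure or testing procedure changes.

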5.3.2 MAS-B of the Finger Flexor Muscle Group

MAS-B of the finger flexor muscle group will be analyzed using the subgroup of patients with wrist identified as the principal muscle group. The average grade change from baseline for weeks 4 and 6 on the MAS-B for finger flexor muscle groups will be summarized by treatment group and analyzed by ANCOVA model with age group, treatment group, study center and previous botulinum toxin exposure as factors and baseline MAS-B of finger flexor muscle group as a covariate. The grade change from baseline at each time point will also be summarized and analyzed in the same fashion. In addition, the frequency distribution of the grade changes from baseline on the MAS-B as well as the percentage of responders (with at least a 1-grade reduction in MAS-B) will be summarized by treatment group at each post-treatment office visit. A logistic regression analysis will also be performed on the responder status at each post-treatment visit with a covariate of baseline MAS-B of finger flexor muscle group and factors of age group, treatment group, study center, and previous botulinum toxin exposure, if applicable.

